## 15 Appendix 3: Specific Renal Alert Criteria and Actions

**Table 15-1 Specific Renal Alert Criteria and Actions**

Serum Event	
Serum creatinine increase 25 – 49% compared to baseline	Confirm 25% increase after 24-48h Follow up within 2-5 days
Acute Kidney Injury: Serum creatinine increase $\geq$ 50% compared to baseline	Follow up within 24-48h if possible Consider study treatment interruption Consider patient hospitalization /specialized treatment
Urine Event	
New dipstick proteinuria $\geq$ 1+ Albumin- or Protein-creatinine ratio increase $\geq$ 2-fold Albumin-creatinine ratio (ACR) $\geq$ 30 mg/g or $\geq$ 3 mg/mmol; Protein-creatinine ratio (PCR) $\geq$ 150 mg/g or $>$ 15 mg/mmol	Confirm value after 24-48h Perform urine microscopy Consider study treatment interruption / or discontinuation
New dipstick glycosuria $\geq$ 1+ not due to diabetes	Blood glucose (fasting) Perform serum creatinine, ACR
New dipstick hematuria $\geq$ 1+ not due to trauma	Urine sediment microscopy Perform serum creatinine, ACR
For all renal events:	
Document contributing factors in the CRF: co-medication, other co-morbid conditions, and additional diagnostic procedures performed Monitor patient regularly (frequency at investigator's discretion) until either: Event resolution: sCr within 10% of baseline or protein-creatinine ratio within 50% of baseline, or Event stabilization: sCr level with $\pm$ 10% variability over last 6 months or protein-creatinine ratio stabilization at a new level with $\pm$ 50% variability over last 6 months.	

## **16 Appendix 4: Guideline for the management of renal dysfunction**

General principles:

Glomerular filtration rate in HF subjects depends on intrinsic renal function and on a balance between afferent and efferent glomerular arterial tonicity. This tonicity is partly regulated by a stimulation of angiotensin II and could be affected by either study medication. Moreover, renal dysfunction may develop or may deteriorate in some subjects after study drug administration. These recommendations have been developed to guide the investigators in managing subjects with renal dysfunction after randomization.

Two types of response to serum creatinine increase are described:

### **Surveillance situation**

If, at any time after randomization, eGFR decreases by  $\geq 25\%$  from baseline (or if serum creatinine concentration increase to 2.5 mg/dL [221  $\mu$ mol/L]), the investigator will check for potentially reversible causes of renal dysfunction such as:

- Non-steroidal anti-inflammatory drug intake, antibiotics, or other treatments known to affect creatininemia
- Volume decrease, including that resulting from excessive dosing of diuretics
- Urinary infection
- Urinary tract obstruction
- Study medication

### **Action situation**

[figure not shown]
If a subjects eGFR decreases by  $\geq 40\%$  from baseline (or if serum creatinine concentration rises above 3 mg/dL (265  $\mu$ mol/L), the investigator will check for potentially reversible causes of renal dysfunction (see above).

[figure not shown]
If the investigator judges that study medication has to be stopped, he/she will have to contact the Novartis medical monitor or his/her designee. Thereafter, serum creatinine assessments will have to be repeated at least each week until levels return to acceptable values. If study medication was stopped, every effort will be done to restart it again, according to clinical conditions.

[figure not shown]
## 17 Appendix 5: Guidelines for the management of blood pressure

[figure not shown]
### Guidelines

[figure not shown]
1. Investigator should monitor blood pressure closely
2. If symptomatic hypotension occurs:
  - a. Correct any treatable cause, e.g. hypovolemia
  - b. If hypotension persists, any antihypertensive drug and non-disease-modifying drugs, such as diuretics, CCBs, nitrates, and  $\alpha$ -blockers, should be down-titrated or stopped first before down-titration of the study drug is considered
3. If hypotension persists, the study drug should be down-titrated or even temporarily withdrawn. The dose re-challenge and medication adjustment guidelines described in [Section 5.5.4](#) should be adhered to as much as possible.

[figure not shown]

[figure not shown]

[figure not shown]

[figure not shown]

[figure not shown]

## 21 Appendix 9: Prohibited Medications: Prescription and non-prescription medications taken for insomnia or to induce sleep

CATAGORY	EXAMPLES
Benzodiazepines with sedating properties for insomnia; or alternative indications taken at bedtime	Examples include: Alprazolam (Xanax) Clonazepam (Clozaril) Diazepam (Valium) Estazolam (Prosom) Flurazepam (Dalmane) Lorazepam (Ativan) Quazepam (Doral) Oxazepam (Serax) Temazepam (Restoril) Triazolam (Halcion)
Non-benzodiazepines for insomnia	Examples include: Eszopiclone (Lunesta) Ramelteon (Rozerem) Suvorexant (Belsomra) Tasimelteon (Hetlioz) Zaleplon (Sonata) Zolpidem (Ambien, Ambien CR, Edluar, Intermezzo, Zolpimist)
Antidepressants with sedating properties for insomnia; or alternative indications taken at bedtime	Examples include: Amitriptyline (Elavil), Doxepin (Silenor, Sinequan) Mirtazapine (Remeron) Trazodone (Oleptro, Desyrel)
Other prescriptions with sedating properties for insomnia; or alternative indications taken at bedtime	Examples include: Baclofen (Lioresal, Gablofen) Cyclobenzaprine (Flexeril) Gabapentin (Neurontin) Hydroxyzine (Atarax) Olanzapine (Zyprexa) Phenobarbital (Phenobarb) Quetiapine (Seroquel) Tiagabine (Gabitril)
Non-prescription Drugs for sleep/insomnia or designated for "nighttime" or "PM" use containing any of the following active ingredients: Diphenhydramine, Doxylamine, Chlorpheniramine	Examples include: Advil P.M. Aleve P.M. Benadryl Chlorphen Nytol Nyquil Sominex Tylenol P.M Unisom ZzzQuil
Non-prescription Herbs/Supplements for sleep/insomnia or designated for "nighttime" or "PM"	Examples include: 5-HTP Kava Kava Melatonin Valerian Root

CRT-P	Cardiac Resynchronization Therapy – No ICD
CRT-D	Cardiac Resynchronization Therapy – With ICD
CSR	Clinical Study report
CTCAE	Common Terminology Criteria for Adverse Events
DCT	Data Collection Tool
eCRF	Electronic Case Report Form
eGFR	Estimated Glomerular Filtration Rate
FAS	Full Analysis Set
H_0	Null Hypothesis
H_A	Alternative Hypothesis
HF	Heart Failure
████████	████████
ICD	Implantable Cardioverter Defibrillator
IRT	Interactive Response Technology
████████	████████
LOCF	Last Observation Carried Forward
MRI	Magnetic Resonance Imaging
MedDRA	Medical Dictionary for Regulatory Activities
NYHA	New York Heart Association
PCI	Percutaneous Coronary Intervention
PD	Pharmacodynamic
PK	Pharmacokinetic
PRO	Patient-reported Outcomes
PT	Preferred Term
RBC	Red Blood Cell

RS	Randomized Set
SAE	Serious Adverse Event
SAP	Statistical Analysis Plan
SOC	System Organ Class
SS	Safety Set
TEAE	Treatment-emergent Adverse Event
TFLs	Tables, Figures, Listings
TIA	Transient Ischemic Attack
████████	████████
USPI	United States Package Insert
WASO	Wake After Sleep Onset
WBC	White Blood Cell
WHO	World Health Organization

1 Introduction

The statistical analysis plan (SAP) will outline in detail the analyses planned in the protocol. The analyses will be used to generate the Clinical Study Report (CSR). The SAP is based on protocol version 02 (amended protocol) dated 13-Mar-2018 and the data collection tool (DCT) version 3.0 dated 04-May-2017.

1.1 Study design

This study is a multicenter, randomized, double-blind, double dummy, parallel group, active-controlled 8-week study with open-label extension using medical device-grade patient worn sensors to measure waking and sleeping physical activity in the ambulatory outpatient setting. The 18-week study duration will consist of a 2-week baseline observation phase (with patients continuing their current heart failure [HF] drug therapy), followed by an 8-week blinded treatment phase during which approximately 136 patients will be randomized to either initiation of sacubitril/valsartan treatment or enalapril comparator in a 1:1 ratio with no stratification at approximately 25-30 centers in the United States, and finally an 8-week open-label extension phase during which all patients will be treated with sacubitril/valsartan.

Each patient will undergo a 36-hour washout period (during which angiotensin converting enzyme inhibitor [ACEi], or study drug will be withheld) before the start of the randomized, blinded treatment phase, and again before beginning the open-label extension phase to ensure that the blinding of the core study is maintained and to reduce the risk of angioedema.

Patients will be randomized to either sacubitril/valsartan 24/26 mg bis in diem/twice a day (BID) or enalapril 2.5 mg BID (Dose Level 1). At each subsequent study visit during the double-blind epoch, the study physician will sequentially up-titrate the study drug dose (based on clinical tolerance and the United States Package Insert [USPI]) to achieve the desired dose of sacubitril/valsartan 97/103 mg BID or enalapril 10 mg BID (Dose Level 3). Dose level 2 is defined as sacubitril/valsartan 49/51 mg BID or enalapril 5 mg BID. Patients not tolerating escalation from Dose Level 1 to Dose Level 2 (or Dose Level 2 to Dose Level 3) can be titrated down to the next lower Dose Level (including active medication and matching placebos), if, in the investigator's judgement, the adjustment/elimination of concomitant medications is not possible or does not alleviate the side effects of concern.

All patients entering the open-label epoch will be given sacubitril/valsartan 49/51 mg BID (Dose Level 2) unless they completed the double-blind treatment epoch on Dose Level 1. Instead, these patients will enter the open-label epoch on sacubitril/valsartan 24/26 mg BID (Dose Level 1). At each subsequent study visit during the open-label epoch, the study physician will sequentially up-titrate the study drug dose (based on clinical tolerance and the USPI) to achieve the targeted desired dose of sacubitril/valsartan 97/103 mg BID (Dose Level 3). Patients not tolerating escalation from Dose Level 1 to Dose Level 2 (or Dose Level 2 to Dose Level 3) can be titrated down to the next lower Dose Level, if, in the investigator's judgement, the adjustment/elimination of concomitant medications is not possible or does not alleviate the side effects of concern.

All eligible patients will be randomized via Interactive Response Technology (IRT) to one of the treatment arms. The investigator or his/her delegate will contact the IRT after confirming that the patient fulfills all the inclusion/exclusion criteria. The IRT will assign a randomization

number to the patient, which will be used to link the patient to a treatment arm and will specify a unique medication number for the first package of study drug to be dispensed to the patient.

The randomization numbers will be generated using the following procedure to ensure that treatment assignment is unbiased and concealed from patients and investigator staff. A patient randomization list will be produced by the IRT provider using a validated system that automates the random assignment of patient numbers to randomization numbers. These randomization numbers are linked to the different treatment arms, which in turn are linked to medication numbers. A separate medication list will be produced by or under the responsibility of Novartis Drug Supply Management using a validated system that automates the random assignment of medication numbers to packs containing the investigational drug(s).

The primary analysis time point will be Week 8 (end of the double-blind period).

There are no interim analyses planned.

1.2 Study objectives and endpoints

The primary objective is to evaluate the effect of initiation of sacubitril/valsartan treatment versus enalapril on physical activity during the waking hours as an objective measure of physical function.

The secondary objective is to evaluate the effect of initiation of sacubitril/valsartan treatment versus enalapril on patients' sleep as an objective measure of physical function.

2 Statistical methods

2.1 Data analysis general information

[REDACTED] a Novartis-designated Contract Research Organization (CRO) will be performing all analyses outlined in this SAP. SAS® version 9.3 (or higher) will be used for all analyses.

Data from all centers that participate in this protocol will be combined, so that an adequate number of patients will be available for analysis.

Unless otherwise specified, for continuous data, the mean, standard deviation, median, first and third quartiles, interquartile range, and minimum and maximum values will be presented. For categorical data, frequencies and percentages will be presented.

All statistical tests will be conducted against a two-sided alternative hypothesis, employing a significance level of 0.05, unless otherwise specified.

All data will be provided in listings in addition to summaries described below.

2.1.1 General definitions

Study treatment

Patients will receive either sacubitril/valsartan or enalapril during the first 8 weeks of the study. Study treatment will refer to either of these two drugs.

Baseline

The last non-missing assessment prior to or on the start date of study treatment (randomization date for patients not treated) will be used as baseline, unless otherwise specified.

Date of first administration of study treatment

Randomized treatment phase: The date of first administration of study treatment in the randomized treatment phase is defined as the first date a dose of study treatment is administered and recorded on the Dosage Administration Record - At Visit (Visit 3) electronic case report form (eCRF).

Open-label extension phase: The date of first administration of study treatment in the open-label extension phase is defined as the first date a dose of sacubitril/valsartan is administered in the open-label extension phase and recorded on the Dosage Administration Record - Summary eCRF.

Date of last administration of study treatment

Randomized treatment phase: The date of last administration of study treatment in the randomized treatment phase is defined as the last date a dose of study treatment is administered in the randomized treatment phase and recorded on the Double-Blind Phase Disposition eCRF (for patients continuing into the open-label extension phase) or the Study Completion/Discontinuation eCRF (for patients not continuing into the open-label extension phase).

Open-label extension phase: The date of last administration of study treatment in the open-label extension phase is defined as the last date a dose of sacubitril/valsartan is administered in the open-label extension phase and recorded on the Dosage Administration Record - Summary eCRF.

Study day

The study day describes the day of the assessment relative to the date of randomization.

The study day will be calculated as the difference between the date of assessment and the date of randomization plus 1. If the date of assessment is prior to the date of randomization, the study day will be negative and will be calculated as the difference between the date of the assessment and the date of randomization.

Randomized treatment phase

Assessments performed at Weeks 2, 4, or 8 (e.g., vital signs) are assigned to the randomized treatment phase for summarization purposes. Unscheduled assessments are not assigned to a phase.

For summarization of adverse events [AEs], medications, protocol deviations, and notable vital signs and laboratory abnormalities by treatment phase, an assessment during the randomized treatment phase is defined as any assessment obtained in the following time interval:

Date of randomization (or date of first administration of study treatment, as appropriate) through the date of the Week 8 visit, inclusive.

Open-label extension phase

Assessments performed at Weeks 10, 12, or 16 (e.g., vital signs) are assigned to the open-label extension phase for summarization purposes. Unscheduled assessments are not assigned to a study phase.

For summarization of AEs, medications, protocol deviations, and notable vital signs and laboratory abnormalities by treatment phase, an assessment during the open-label extension phase is defined as any assessment obtained in the following time interval:

After the date of the Week 8 visit.

Last contact

The date of last contact will be the last visit date for each patient and will be derived by examining all visit data collected in the eCRFs.

Year, month and week

For reporting purposes, the rules below will be followed to convert a year, month and week to days.

1 year = 365.25 days

1 month = 30.3475 days

1 week = 7 days

1 day = 24 hours

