### 3.2 Rationale for study design

The design of the study facilitates the assessment of change in sequential daily physical activity, [REDACTED] HF symptoms and health-related quality of life; between baseline to select time point assessment periods after randomized, blinded assignment to treatment with sacubitril/valsartan versus the active comparator enalapril. Assessment of the primary endpoint at 8 weeks captures the early impact of initiation of sacubitril/valsartan versus enalapril, which is the focus of the study.

Waking activity will be the primary endpoint, and sleep activity (a measure of sleep disturbance) is the secondary endpoint. Actigraphy, which has been well characterized for the measurement of both daytime and sleep physical activity variables, will be used to inform the primary and secondary endpoints.

[figure not shown]
Prior to randomization, there will be a 2 week phase where device familiarization and baseline assessment will be completed. The initial baseline week will provide an opportunity for the subjects to become familiar and acclimated to the testing devices and assessment routines, prior to entering the baseline phase of the study. Data from the second week of this phase, the 'baseline phase' (Week -1) will be considered as the baseline value for comparison to subsequent periods. Data collected outside of the defined measurement periods will be excluded from analysis for the defined study endpoints.

The 36-hour wash-out interval after randomization and before entering the open-label extension is required per the FDA approved USPI label because there is a potential for increased risk for angioedema in subjects who receive both an ACE inhibitor and the combination of sacubitril/valsartan.

The randomized comparison phase of 8 weeks provides the direct assessment of the initial and early changes associated with sacubitril/valsartan treatment to treatment with the active comparator enalapril.

The open label phase of 8 weeks provides the opportunity for every subject to receive sacubitril /valsartan. This results in one group of subjects that will receive sacubitril/valsartan for a total of 16 weeks, providing information on the endpoints after this duration of continuous therapy. It also provides the opportunity to evaluate changes after initiating sacubitril/valsartan in a group of subjects who all had been previously receiving enalapril treatment for 8 weeks.

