### **9.2 Subject demographics and other baseline characteristics**

Baseline value is defined as the last non-missing assessment prior to the first dose of randomized study medication, unless specified otherwise in the protocol.

Summary statistics will be provided by treatment group for demographics and baseline characteristics. Categorical variables will be summarized using frequency and percentage.

The Randomized Set and FAS will be the subject sets for the above analyses.

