2.7.2 Statistical hypothesis, model, and method of analysis

During the randomized treatment phase, change from baseline for each secondary endpoint will be analyzed at each time point using the same ANCOVA model as for the primary endpoint.

During the open-label extension phase, change from baseline (mean of Week -1) for each secondary endpoint will be analyzed at each time point using paired t-tests for the group randomized to sacubitril/valsartan. The analyses will be repeated using the Week 8 measurement as baseline for the group randomized to enalapril.

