2.8.3 Laboratory data

Laboratory values will be summarized using shift tables (from baseline to most extreme post baseline value) by each laboratory parameter at its worst severity by treatment phase (see Section 2.1.1 for treatment phase definitions). The number and percentage of patients with

laboratory values will be presented by low/normal/high (low and high) classifications to compare baseline to worst post baseline value.

In addition, laboratory values and the change from baseline for each parameter by visit will be summarized by treatment group for both the randomized treatment and open-label extension phases. In the event there are multiple laboratory values within a visit, the worst value will be summarized.

A separate summary table will be presented by treatment phase (see Section 2.2.1 for treatment phase definitions) with the number and percentage of patients having notable lab abnormalities based on percent change from baseline (see Section 5.3 for a list of notable laboratory abnormalities).

Listings of all laboratory values will be provided. A separate listing for pregnancy tests will also be provided. Any notable laboratory abnormalities will be flagged.

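### For patients switching from enalapril, the open-label laboratory and vital-sign tables have no Week 8 baseline, so shift and notable-value counts mix change on enalapril with change after the switch

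*SAP*

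**What the plan says.** SAP 2.1.1 sets the general rule for baseline as "The last non-missing assessment prior to or on the start date of study treatment". Other sections may name a different one, and for patients never treated the date of randomization takes the place of the first dose. The same section describes study treatment as the drug received in the first 8 weeks. Protocol 9.2 leaves no doubt about the anchor: "Baseline value is defined as the last non-missing assessment prior to the first dose of randomized study medication". SAP 2.1.1 also defines a first-dose date for the open-label phase, but does not tie any baseline to it.

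SAP 2.8.3 plans three laboratory displays that use baseline:
- shift tables from baseline to the most extreme later value, by treatment phase;
- by-visit summaries, in which "the change from baseline for each parameter by visit will be summarized by treatment group for both the randomized treatment and open-label extension phases";
- a table, by phase, of the "number and percentage of patients having notable lab abnormalities based on percent change from baseline".

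SAP 2.8.4.1 plans by-visit change and notable values for vital signs in the same way. The limits are in SAP 5.3.2 and 5.4.1. None of these sections names another baseline. For the phase-level tables, the open-label phase is any assessment "After the date of the Week 8 visit".

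For open-label actigraphy the plan does more. SAP 2.7.2 states: "The analyses will be repeated using the Week 8 measurement as baseline for the group randomized to enalapril".

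**The concern.** In the open-label phase every patient is assigned sacubitril/valsartan. In the arm that has taken it since randomization, change from the original baseline is change on that drug. In the enalapril arm it is the sum of 8 weeks on enalapril and whatever followed the switch. A count of notable values from that sum does not show which period produced them.

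Protocol 3.6 names renal dysfunction, hyperkalemia and hypotension as the major risks of sacubitril/valsartan. Creatinine, potassium and systolic pressure are therefore the variables for which a reader would want to know what appeared after the switch. Protocol 9.5.2 rests the safety assessment partly on laboratory abnormalities, and the planned analysis of them is descriptive, so these counts carry weight.

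**Working it through.** **Which baseline applies.** The protocol anchors baseline to the first randomized dose. The SAP's fallback for untreated patients is the randomization date. Both rule out reading baseline as phase-specific, and the safety sections do not use the SAP's option to specify otherwise.

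**What the rules do to individual patients.** Inputs are the SAP 5.3.2 and 5.4.1 limits: potassium up or down more than 20%, creatinine up more than 50%, and systolic pressure below 90 mmHg with a fall of more than 20 mmHg. Percent change = 100 × (open-label value / reference − 1). The patients are hypothetical.

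| Patient | Baseline | Week 8 | Open-label | From original baseline | From Week 8 |
|---|---|---|---|---|---|
| A, potassium | 4.2 | 5.1 | 5.1 | 5.1/4.2: +21.4%, notable | 0%, not notable |
| B, creatinine | 1.0 | 1.6 | 1.6 | 1.6/1.0: +60%, notable | 0%, not notable |
| C, systolic pressure | 112 | 88 | 88 | fall of 24, notable | fall of 0, not notable |
| D, potassium | 4.6 | 4.2 | 5.1 | 5.1/4.6: +10.9%, not notable | 5.1/4.2: +21.4%, notable |
| E, systolic pressure | 112 | 95 | 88 | fall of 24, notable | fall of 7, not notable |

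A, B and C did not change after the switch. Each is notable at Week 8, which belongs to the randomized phase, and is counted again in the open-label phase. D changed only after the switch and is missed. E changed in two steps and is seen only from the original baseline. Neither baseline is sufficient alone.

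**How large it could be.** The documents give no potassium or creatinine variability, so every input here is an assumption:
- true potassium level has mean 4.4 and between-patient SD 0.35;
- each measurement, including Week 8, has visit noise with SD 0.25;
- on enalapril the level shifts by m plus an individual response with SD 0.2, and stays there;
- the switch has no effect;
- a patient is notable if Week 10 or Week 16 differs from the reference by more than 20% in either direction.

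With 400,000 simulated patients, and counts for at most 68 (the planned arm size, with no drop-out):

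| Lasting shift m (mEq/L) | From original baseline | From Week 8 | Patients out of 68 |
|---|---|---|---|
| 0 | 6.1% | 3.2% | 68 × 0.061 = 4.1 vs 68 × 0.032 = 2.2 |
| 0.2 | 10.6% | 2.4% | 7.2 vs 1.6 |
| 0.4 | 21.1% | 1.8% | 14.3 vs 1.2 |

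Of the high flags against the original baseline, 27%, 35% and 44% were already above the limit at Week 8. The others combine a lasting shift with visit noise.

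**Whether the data exist.** Protocol Table 6-1 schedules laboratory tests at Visit 8 (Week 8), then at Weeks 10 and 16. Vital signs are taken at every office visit. Protocol 5.5.4 has open-label drug dispensed at Week 8 but not started until after the 36-hour washout, so the Week 8 value normally precedes the first open-label dose.

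**The case against.** A fixed pre-treatment baseline is a legitimate and conservative choice for safety, and patient E shows why it should stay. Moving the enalapril group to Week 8 alone would hide cumulative change and put the two arms on different baselines. That objection stands and shapes the fix.

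The plan also offers partial remedies. By-visit laboratory and vital-sign values are summarized by treatment group, so the enalapril group's Week 8 level can be read beside later visits. All laboratory values are listed with notable ones flagged. With about 68 patients and two scheduled open-label laboratory visits, carry-over can be traced by hand. A reader might infer that the outputs cannot separate the two periods at all, and that is too strong. The mixing is confined to by-visit change from baseline, where the Week 8 column helps, and to the aggregate shift and notable-value tables, where nothing does.

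A reader might also infer that the protocol promises re-baselined safety tables, because Protocol 3.2 speaks of the chance to "evaluate changes after initiating sacubitril/valsartan in a group of subjects who all had been previously receiving enalapril treatment". The surrounding text is about the study endpoints, and the actigraphy analysis in SAP 2.7.2 already serves it. The passage supports the usefulness of a Week 8 reference but does not commit the plan to one for safety.

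**Conclusion.** The point stands as a cheap improvement to descriptive output. Followed as written, the enalapril group's open-label laboratory shift tables and laboratory and vital-sign notable-value tables mix two treatment periods, with error in both directions. No endpoint, test or decision rule changes.

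A reader might infer that all open-label safety reporting is affected. It is not. Adverse events are placed by onset date and phase, deaths are split by phase, and heart failure signs are tabulated by visit without change from baseline (SAP 2.1.1, 2.8.1.2, 2.8.2, 2.8.4.2).

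A reader might also infer a very large distortion. A simpler model that puts no separate visit noise on the Week 8 value gives 9.1% to 13.1% notable potassium against the original baseline and 0.5% to 1.1% against Week 8. It treats all Week 8 noise as lasting change, so it flatters the Week 8 reference and should not be relied on. With visit noise included, the gap is about twofold (6% against 3%) when enalapril causes no mean shift, and it widens only if a shift is assumed. The documents do not support a particular shift: patients continue their heart failure therapy through baseline, and SAP 2.4.2 includes a category for those currently taking an ACE inhibitor or ARB. The conclusion rests on the baseline definition; the percentages only illustrate it.

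**What to change.** In SAP 2.8.3 and 2.8.4.1, add for the group randomized to enalapril a second set of open-label tables (change, notable values and, for laboratory data, shifts). Use as baseline the last value before the first open-label dose, normally Week 8. This matches the approach in SAP 2.7.2. Keep the original-baseline tables for both groups so that cumulative changes remain visible. State in SAP 2.1.1 which baseline each table uses, and show the open-label tables by randomized group.

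The cost is one derived baseline flag, a few more descriptive tables, and two baselines that need clear labels. No new data are needed.
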